## 7.2 Serious Adverse Events

An AE or adverse reaction is considered serious if, in the view of either the Investigator or the Sponsor, it results in any of the following outcomes:

- Death
- A life-threatening AE

Note: An AE or adverse reaction is considered “life-threatening” if, in view of either the Investigator or the Sponsor, its occurrence places the subject at immediate risk of death. It does not include an event that, had it occurred in a more severe form, might have caused death.

- Requires hospitalization or prolongation of existing hospitalizations

Note: Any hospital admission with at least one overnight stay will be considered an inpatient hospitalization. An emergency room or urgent care visit without hospital admission will not be recorded as a SAE under this criterion, nor will hospitalization for a procedure scheduled or planned before signing of informed consent, or elective treatment of a pre-existing condition that did not worsen from Baseline. However, unexpected complications and/or prolongation of hospitalization that occur during elective surgery should be recorded as AEs and assessed for seriousness. Admission to the hospital for social or situational reasons (i.e., no place to stay, live too far away to come for hospital visits, respite care) will not be considered inpatient hospitalizations.

- A persistent or significant disability/incapacity or substantial disruption of the ability to conduct normal life functions
- A congenital anomaly/birth defect
- An important medical event.

Note: Important medical events that do not meet any of the above criteria may be considered an SAE when, based upon appropriate medical judgment, they may jeopardize the subject and may require medical or surgical intervention to prevent one of the outcomes listed above. Examples of such medical events include allergic bronchospasm requiring intensive treatment in an emergency room or at home, blood dyscrasias or convulsions that do not result in inpatient hospitalizations, or the development of drug dependency.

## 7.3 Serious Adverse Event Reporting – Procedures for Investigators

### Initial Reports

All SAEs occurring from the time the subject signs the informed consent until 30 days following the last administration of study drug must be reported to CRO within 24 hours of the knowledge of the occurrence. After the 30-day reporting window, any SAE that the Investigator considers related to study drug must be reported to CRO or designee.

To report the SAE, complete the AE form electronically in the eCRF for the study and then the paper SAE report form. Send the paper SAE report form via email to the CRO    Personal Protected Data

#### Personal Protected Data

within 24 hours of awareness regardless of the relationship to the study drug. The SAE report form should be completed as thoroughly as possible; however, submission of the report should not be delayed if information is not available at the time of the initial report.

#### Follow-Up Reports

The Investigator must continue to follow the subject until the SAE has subsided or until the condition becomes chronic in nature, stabilizes (in the case of persistent impairment), or the subject dies.

Within 24 hours of receipt of follow-up information, the Investigator must update the paper SAE report form and the AE form electronically in the eCRF and submit any supporting documentation (e.g., patient discharge summary or autopsy reports) to CRO via fax or email.

#### **7.4      Pregnancy Reporting**

If a subject becomes pregnant during the study, the Investigator is to stop dosing with study drug immediately and the subject should be withdrawn from the study. Early Termination study visit procedures as indicated in the SOA should be implemented at that time.

A pregnancy is not considered to be an AE or SAE; however, it must be reported to the CRO within 24 hours of knowledge of the pregnancy during the study or up to 90 days after the last dose of study drug via the Pregnancy Data Collection Form. The Investigator must complete the Pregnancy Data Collection Form and fax or email it to the CRO (contact information listed in [Section 7.6](#)).

If the female partner of a male subject becomes pregnant while the subject is receiving study drug or up to 90 days after the last dose of study drug, the Investigator should notify the CRO as described above.

The pregnancy should be followed until the outcome of the pregnancy, whenever possible. Once the outcome of the pregnancy is known, the Pregnancy Data Collection Form should be completed and faxed or emailed to the CRO (contact information listed in [Section 7.6](#)). If the outcome of the pregnancy meets the criteria for immediate classification as an SAE (i.e., postpartum complication, spontaneous abortion, stillbirth, neonatal death, or congenital anomaly), the Investigator should follow the procedures for reporting an SAE.

#### **7.5      Expedited Reporting**

The CRO will report all relevant information about Suspected Unexpected Serious Adverse Reactions (SUSAR) that are fatal or life-threatening as soon as possible to the Food and Drug Administration (FDA), and in any case no later than 7 days after knowledge by the CRO of such a case. Relevant follow-up information will subsequently be communicated within an additional 8 days.

All other SUSARs will be reported to the FDA as soon as possible but within a maximum of 15 days of first knowledge by the CRO.

The CRO will also report any additional expedited safety reports required in accordance with the relevant timelines.

The CRO will also inform all Investigators as required per local regulation.

The requirements above refer to the requirements relating to investigational medicinal product.

## 7.6 Special Situation Reports

Special situation reports include reports of overdose, misuse, abuse, medication error, and reports of adverse reactions associated with product complaints.

- **Overdose:** Refers to the administration of a quantity of a medicinal product given per administration or cumulatively (accidentally or intentionally), which is above the maximum recommended dose according to the protocol. Clinical judgement should always be applied. In cases of a discrepancy in the drug accountability, overdose will be established only when it is clear that the subject has taken additional dose(s), or the Investigator has reason to suspect that the subject has taken additional dose(s).
- **Misuse:** Refers to situations where the medicinal product is intentionally and inappropriately used that is not in accordance with the protocol instructions or local prescribing information and may be accompanied by harmful physical and/or psychological effects.
- **Abuse:** Is defined as persistent or sporadic, intentional excessive use of a medicinal product, which is accompanied by harmful physical or psychological effects.
- **Medication error:** Is any unintentional error in the prescribing, dispensing, or administration of a medicinal product by a healthcare professional, subject, or consumer, respectively. The administration or consumption of the unassigned treatment and administration of an expired product are always reportable as medication errors. Cases of subjects missing doses of investigational product are not considered reportable as medication error.

All special situation events as described above must be reported on the Special Situations Report form and faxed or emailed to the CRO (contact information listed below) within 24 hours of knowledge of the event. All AEs associated with these Special Situation reports should be reported as AEs or SAEs as well as recorded on the AE eCRF and/or the paper SAE report form. Details of the symptoms and signs, clinical management, and outcome should be provided, when available.

CRO Clinical Safety Contact Information:  
Premier Research Pharmacovigilance (PV)

Personal Protected Data

## 7.7 Physical and Neurological Examinations

A complete physical examination (PE) will include general observations; head, eyes, ears, nose, and throat (HEENT); cardiovascular; respiratory; abdomen; skin; extremities; lymphatic system; and musculoskeletal. Height, weight, CCI will also be measured and

recorded. A symptom-based PE will be performed at Baseline/Pre-dose and Day 21 Follow-up visits only (includes: general, HEENT, cardiovascular, respiratory, abdomen, skin, extremities).

Investigators should pay special attention to clinical signs related to previous serious illnesses.

Neurological examinations will include assessment of mental status, cranial nerves, motor, sensory, reflexes, coordination, and gait. In addition to the complete neurological exam, a focused neurological exam is conducted during the Screening visit to include full assessment of tremor per Movement Disorder Society classification criteria ([Bhatia, 2018](#)).

Physical and neurological exams will be conducted at timepoints indicated in the SOA ([Appendix A, Table 2](#)).

## **7.8        Electrocardiograms**

Triplet 12-lead ECG will be obtained as indicated in the SOA ([Appendix A, Table 2](#)), using an ECG machine that automatically calculates the heart rate and measures PR, QRS, QT, and QTcF intervals. ECGs are to be assessed **prior** to vital signs and blood sampling for laboratory tests. Triplet ECG recordings will be taken, after a minimum of 5 minutes of rest in supine position: 3 consecutive recordings will be made in succession, no more than 2 minutes apart. The full set of triplicates should be completed in less than 4 minutes. These ECGs will be read by the Investigator to rule out any clinically significant findings. An ECG is to be taken at the Screening, Baseline/Pre-dose, Day 1, Day 7, Day 14 and Day 21 Follow-up visits. At the Day 1, Day 7 and Day 14 visits, ECGs are to be obtained at the following time points: 30min, 60min, and 2 hours following the first dose of the day and again 30 min, 60 min, 2 hours and 4 hours after the second dose of study drug in the clinic. On Days 7 and 14, an ECG is to be taken at 30 min, 60 min, 2 hours, and 4 hours following the dose of study drug in the clinic. There is a +/- 5-minute allowable window for these ECGs.

After a minimum of 5 minutes of rest in supine position, 3 consecutive recordings should be made in succession, no more than 2 minutes apart. The full set of triplicates should be completed in less than 4 minutes. These ECGs will be read by the Investigator to rule out any clinically significant findings.

## **7.9        Vital Signs**

Vital signs (VS) assessments (to be taken before blood collection for laboratory tests) will be assessed and include blood pressure (systolic and diastolic), heart rate, respiratory rate and oral temperature. Vital signs are to be taken at the Screening, Baseline/Pre-dose, Day 1, Day 7, Day 14 and Day 21 Follow-up visits. The vital signs on Day 1 are to be taken at 30min, 60min, and 2 hours following the first dose of the day and again 30 min, 60 min, 2 hours and 4 hours after the second dose of study drug in the clinic. On Days 7 and 14, the vital signs are to be taken at 30 min, 60 min, 2 hours, and 4 hours following the dose of study drug in the clinic. There is a +/- 5-minute allowable window for these vital signs.

## **7.10       Orthostatic Vital Signs**

Orthostatic vital signs will be measured at Screening, Baseline, Day 1, Day 7, Day 14 and during the Follow-up visit.

During the Screening visit, orthostatic VS measurements will be done once, at any time during the visit.

During the Baseline/Pre-Dose visit, baseline orthostatic VS will include 3 separate measurements with each measurement of blood pressure and heart rate separated from the next by at least 15-20 minutes apart, to minimize the potential impact of biological variability of a single baseline measurement. The average of the 3 baseline orthostatic VS measurements will be used for comparison to all post-treatment measurements.

During Day 1, orthostatic VS measurements will be done twice, 2 to 4 hours following each in-clinic dose.

During Day 7 and Day 14 visits, orthostatic VS measurements will be done once, 2 to 4 hours following the in-clinic dose.

During the Follow-up visit, orthostatic VS measurements will be done once, at any time during the visit.

Orthostatic VS must be assessed using an appropriate device, and the arm position must be standardized for each subject. These measurements are to be taken in the same arm for the duration of the study. The position of the cuff on the arm should be in line with the heart with the arm lying next to the subject when semi-supine and should be in line with the heart at approximately a 45 degrees angle from horizontal for the standing measure.

In order to obtain orthostatic VS, the subjects will undergo the following procedures in sequential order:

1. The subject will rest in a supine or semi-supine position for at least 5 minutes.
2. After remaining supine or semi-supine for 5 minutes, one measurement of blood pressure and heart rate will be taken.
3. The subject will then be asked to sit on the edge of the bed/chair with feet on the floor (or with feet dangling from the bed/chair depending on the height of the bed/chair) for approximately 30 seconds.
4. The person performing the assessment will then ask the question, “Are you ready to stand?”
  - If the subject responds in the affirmative, the subject will proceed to stand and then be asked to remain standing for 2 minutes. After standing for 2 minutes, blood pressure and heart rate will be recorded.
  - If the subject states that he or she is not ready to stand, the subject will be allowed to sit as positioned for one additional minute and will be asked again if they are ready to stand. The subject will proceed to stand. After standing for 2 minutes, one measurement will be taken for blood pressure and heart rate.
  - If the individual is still unable to stand, vital signs will be measured while the subject is in an upright seated position.

Orthostatic hypotension will be defined as a reduction in SBP of 20 mmHg or more, and/or a reduction in DBP of 10 mmHg or more, for the standing measurement compared to the supine or semi-supine measurement. If orthostatic hypotension is suspected, the measurement process may be repeated at the Investigator's discretion. Any confirmed orthostatic hypotension or clinically significant measurements that are associated with clinical symptoms will be recorded as adverse events.

If routine VS and orthostatic VS coincide at the same time points, the same values for routine VS (blood pressure and heart rate) during the supine or semi-supine position should be recorded in the CRFs as the same values of the start of orthostatic VS in the supine or semi-supine position.

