## 4. Statistical Analysis and Reporting

### 4.1. Introduction

Data processing, tabulation of descriptive statistics, calculation of inferential statistics, and graphical representations will be performed primarily using SAS (release 9.4 or higher).

Commercially Confidential Information If the use of other software is warranted, the final statistical methodology report will detail what software was used for what purposes.

Continuous (quantitative) variable summaries will include the number of subjects (n) with non-missing values, mean, standard deviation (SD), median, minimum, and maximum.

Categorical (qualitative) variable summaries will include the frequency and percentage of subjects who are in the particular category for each possible value. In general, the denominator for the percentage calculation will be based upon the total number of subjects in the study population, unless otherwise specified. The denominator for by-visit displays will be the number of subjects in the relevant study population with non-missing data at each visit. If there is any missing value for a categorical analysis, a “Missing” category will be displayed as the last category in the table for the variable.

For weight, height, CCI one decimal place will be used for all summary statistics. For all other summaries, the minimum and maximum will be reported with the same degree of precision (i.e., the same number of decimal places) as the observed data. Measures of location (mean and median) and confidence interval boundaries will be reported to 1 degree of precision more than the observed data, up to 3 decimal places. Measures of spread (SD) will be reported to 2 degrees of precision more than the observed data, up to 3 decimal places.

Percentages will be presented to 1 decimal place, unless otherwise specified. Percentages equaling 0 or 100 will be displayed with no decimal places or percentage symbols.

Fractional numeric values will be presented with a zero to the left of the decimal point (for example, 0.12 – 0.30).

Unless otherwise indicated, all statistical tests will be conducted at the 0.05 significance level using 2-tailed tests, and *P* values will be reported. Corresponding 95% confidence intervals (CIs) will be presented for statistical tests, where applicable.

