### 9.3. Vital Signs

Descriptive summaries of observed values and changes from baseline will be calculated for supine systolic blood pressure (SBP), standing SBP, supine diastolic blood pressure (DBP), standing DBP, supine heart rate (HR), standing HR, respiration rate, and oral temperature by study visit for the Safety Population overall and by cohort. Shifts from baseline for SBP, DBP, and HR values below, within, or above the normal range will be provided by study visit for the Safety Population overall and by cohort. Vital sign parameters outside the normal range will be flagged in the listings. The mean change from baseline in each parameter will also be plotted by study visit. Abnormal vital signs are as follows:

Commercially Confidential Information

- SBP >140 mmHg
- SBP <90 mmHg
- DBP >90 mmHg
- DBP <60 mmHg
- HR >100 bpm
- HR <60 bpm
- Respiration rate >20 breaths/min
- Respiration rate <12 breaths/min
- Oral temperature >99.1 °F/37.2 °C
- Oral temperature <97.8 °F/36.5 °C

Orthostatic vital signs (blood pressure and heart rate) will also be summarized by position and study visit and by cohort. During the Pre-dose visit, baseline orthostatic vital signs will include 3 separate measurements and the average of the 3 baseline orthostatic vital signs measurements will be used for comparison to all post-treatment measurements. The average HR, SBP, and DBP will be presented in the pre-dose baseline summaries and each of the individual measurements will be listed for that study visit.

Orthostatic hypotension will be defined as a reduction in systolic blood pressure of 20 mmHg or more and/or a reduction in diastolic blood pressure of 10 mmHg or more, for the standing measurement compared to the supine or semi-supine measurement. The frequency and percentage of subjects with orthostatic hypotension will also be presented by cohort. Any confirmed orthostatic hypotension or clinically significant measurements that are associated with clinical symptoms will be recorded as AEs. Orthostatic vital signs parameters outside the ranges specified above will be flagged in the listings.

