**Same shell as Table 14.3.5.1.1**

**Programming note:** Visits include Screening, Baseline, Day 1, Day 7 Post-Dose, Day 14 Post-Dose, and Day 21; parameters include Standing Systolic Blood Pressure (mmHg), Supine Systolic Blood Pressure (mmHg), Supine Heart Rate (bpm), Standing Heart Rate (bpm), Standing Diastolic Blood Pressure (mmHg), and Supine Diastolic Blood Pressure (mmHg); SOURCE: Listing 16.2.8.3.1, Listing 16.2.8.3.2.

Table 14.3.6.1.4  
Shift from Baseline in Orthostatic Vital Signs by Study Visit  
Safety Population

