Reduction of SBP of 20 mmHg or more	XX (XX.X%)	XX (XX.X%)	XX (XX.X%)
Reduction of DBP of 10 mmHg or more	XX (XX.X%)	XX (XX.X%)	XX (XX.X%)
Day 14 Post-Dose			
Reduction of SBP of 20 mmHg or more	XX (XX.X%)	XX (XX.X%)	XX (XX.X%)
Reduction of DBP of 10 mmHg or more	XX (XX.X%)	XX (XX.X%)	XX (XX.X%)
Day 21			
Reduction of SBP of 20 mmHg or more	XX (XX.X%)	XX (XX.X%)	XX (XX.X%)
Reduction of DBP of 10 mmHg or more	XX (XX.X%)	XX (XX.X%)	XX (XX.X%)

Abbreviations: DBP = diastolic blood pressure; SBP= systolic blood pressure.

Note: Percentages are n/Number of subjects in the Safety Population and respective Protocol Amendment\*100. Orthostatic hypotension is defined as a reduction in SBP of 20 mmHg or more, and/or a reduction in DBP of 10 mmHg or more, for the standing measurement compared to the supine or semi-supine measurement.

[1] The average of the 3 baseline orthostatic vital signs measurements will be used for comparison to all post-treatment measurements.

SOURCE: Listing 16.2.8.3.2

Table 14.3.6.2.1  
Summary of 12-Lead Electrocardiogram by Study Visit  
Safety Population

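### No rule says how to classify a subject who could not stand and has only a seated reading: the subject cannot be counted as orthostatic hypotension, and the SAP treats the subject as a non-case in one place and as missing in another

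*Protocol*

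**What the plan says.** **Procedure.** In Protocol 7.10 the subject rests supine or semi-supine, has blood pressure and heart rate taken, sits briefly, and is then asked to stand. A subject who is not ready gets one more minute. After that: "If the individual is still unable to stand, vital signs will be measured while the subject is in an upright seated position". Such a subject therefore has a supine and a seated reading, but no standing one.

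**Definition.** Still in 7.10, OH is a systolic fall of at least 20 mmHg, a diastolic fall of at least 10 mmHg, or both, "for the standing measurement compared to the supine or semi-supine measurement". SAP 6.1.8, SAP 9.3, the note to Table 14.3.6.1.6 ("Orthostatic hypotension is defined as a reduction in SBP of 20 mmHg or more") and the footnote to Listing 16.2.8.3.2 repeat the standing-based definition. None gives a seated version.

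**Planned summaries.** SAP 9.3: "The frequency and percentage of subjects with orthostatic hypotension will also be presented by cohort". Table 14.3.6.1.6 does this by visit, with one row for the systolic criterion and one for the diastolic criterion. It has no combined row and no Missing row. Table 14.3.6.1.3 covers two positions: "parameters include Standing Systolic Blood Pressure (mmHg), Supine Systolic Blood Pressure (mmHg", with the matching heart rate and diastolic entries.

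**Denominators.** The note to Table 14.3.6.1.6 reads: "Percentages are n/Number of subjects in the Safety Population and respective Protocol Amendment". SAP 4.1 reads: "The denominator for by-visit displays will be the number of subjects in the relevant study population with non-missing data at each visit". It adds that where a categorical value is missing, a Missing "category will be displayed as the last category in the table for the variable".

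**The concern.** The procedure foresees an outcome that the definition cannot handle. A subject who could not stand has no standing value, so the standing-minus-supine difference cannot be calculated and neither criterion can be met, whatever the seated pressure shows.

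This would matter little if inability to stand had nothing to do with blood pressure. After a dose it may be related to orthostatic intolerance. In that case the missing standing value carries information about the outcome being counted, and the error runs one way, towards too few cases.

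The display is not incidental. Safety is the primary objective. OH has its own procedure, three baseline readings, two post-dose readings on Day 1, an exclusion for any lifetime history, and its own table. A reader of Table 14.3.6.1.6 could not tell a subject who stood with stable pressure from one who could not stand.

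**Working it through.** The plan states no OH rate, threshold or power for this measure, so there is no figure to reproduce. The check has two parts.

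**1. Trace one record through the rules.** Take a subject at a post-dose visit with supine and seated readings and no standing reading.

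| Rule | Result for this subject |
|---|---|
| OH definition (Protocol 7.10; SAP 6.1.8, 9.3) | Standing-minus-supine difference undefined; criteria cannot be met |
| Table 14.3.6.1.6, numerator | Not counted in the systolic or the diastolic row |
| Table 14.3.6.1.6, note | Stays in the Safety Population denominator; no Missing row; implicit non-case |
| SAP 4.1 | Leaves the by-visit denominator; shown as Missing |
| Table 14.3.6.1.3 | Seated value has no parameter |

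The two denominators disagree on whether the subject is a non-case or missing. They agree that the subject is not in the numerator.

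**2. Size.** Inputs:
- N = 30 (Protocol 11.2.4, approximate).
- x = subjects meeting the standing definition at a visit: assumed 0 to 3.
- u = subjects unable to stand at that visit: assumed 1 to 3.

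Neither x nor u is in the documents. Three quantities are compared:
- A, Table 14.3.6.1.6 note: x / N
- B, SAP 4.1: x / (N − u)
- C, outer bound if every subject unable to stand were a case: (x + u) / N

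Exact (Clopper-Pearson) 95% intervals are in brackets.

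| x | u | A | B | C |
|---|---|---|---|---|
| 0 | 1 | 0/30 = 0% (0–11.6) | 0/29 = 0% (0–11.9) | 1/30 = 3.3% (0.1–17.2) |
| 0 | 3 | 0/30 = 0% (0–11.6) | 0/27 = 0% (0–12.8) | 3/30 = 10.0% (2.1–26.5) |
| 2 | 1 | 2/30 = 6.7% (0.8–22.1) | 2/29 = 6.9% (0.8–22.8) | 3/30 = 10.0% (2.1–26.5) |
| 2 | 2 | 2/30 = 6.7% (0.8–22.1) | 2/28 = 7.1% (0.9–23.5) | 4/30 = 13.3% (3.8–30.7) |
| 3 | 3 | 3/30 = 10.0% (2.1–26.5) | 3/27 = 11.1% (2.4–29.2) | 6/30 = 20.0% (7.7–38.6) |

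C − A = u/N, which is 1/30 = 3.3 points per subject. C − B = (u/N) × (N − u − x)/(N − u), which is never larger. With x = 2 and u = 2 it is (2/30) × (26/28) = 6.2 points, against 2/30 = 6.7 points for C − A.

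The choice between A and B is therefore minor (6.7% against 7.1% in that example). What matters more is whether these subjects are visible at all.

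The figures describe a single count at one visit in the overall column. Because the shell shows the systolic and diastolic criteria separately, they need not match a particular cell. C is a bound, not an estimate. Within a cohort each subject weighs more, but cohort sizes are not given.

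**The case against.** **The general rules already make the subject missing.** SAP 4.1, 13 and 14.1 all call for a Missing category. The neighbouring Table 14.3.6.1.5 has a Missing row, and Listing 16.2.8.3.2 allows a not-applicable entry in its OH column. The Safety Population note appears under many shells and may be boilerplate. This stands as far as it goes: the documents conflict, and they do not settle on non-case. But a general Missing row would merge inability to stand with a skipped measurement, and the subject would still be absent from the numerator.

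**Symptomatic cases are caught elsewhere.** Protocol 7.10 makes clinically significant measurements with symptoms adverse events, with no standing value required, and treatment-emergent events are the primary endpoint. That is a real safeguard. It depends on the investigator's judgment and does not correct the OH table.

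**The event may be rare.** Apart from tremor, subjects must be otherwise healthy, and any lifetime OH is excluded. This stands; no frequency is stated.

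**The seated value is not lost.** SAP 6.1.9 lists all collected data, Listing 16.2.8.3.2 has a position column, and SAP 9.3 summarises by position. A seated value can therefore be listed, although neither that listing shell nor Table 14.3.6.1.3 names a seated position.

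**A stronger reading is tempting:** that the worst-affected subjects are recorded as free of OH. The documents do not support it. Protocol 7.10 gives no reason for inability to stand and ranks no one by severity, so not every such subject need have OH. The non-case outcome follows only from one table note. Nor do the documents say that a subject who stands but sits before the two-minute reading gets the seated fallback; on that they are silent.

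**Conclusion.** The gap is real but limited. The seated fallback, the standing-only definition and the absence of any rule connecting them are plain in the text. As written, a subject without a standing reading cannot be counted as OH under either denominator. The non-case or missing status is an unresolved conflict between the note to Table 14.3.6.1.6 and SAP 4.1.

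The possible downward bias is at most 3.3 percentage points per such subject in the overall column. That rests on N = 30 and on inability to stand being related to orthostatic intolerance. The plan neither states nor excludes that relation. The conclusion also assumes that sites do not enter a seated value in a standing field; the case report form is not available to check.

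The primary adverse-event endpoint is not shown to be compromised. What is affected is a dedicated descriptive safety table, and the correction is cheap enough to be worth making.

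**What to change.** 1. In SAP 9.3 and Table 14.3.6.1.6, add a row at each visit for subjects unable to stand or with no standing reading, kept apart from other missing data.
2. Reconcile the denominator: either the table note follows SAP 4.1, or SAP 4.1 names this table as an exception. State which applies.
3. Show the OH count with and without these subjects as a sensitivity display, labelled as a bound and not as a diagnosis.
4. Add seated as a position in Table 14.3.6.1.3 and Listing 16.2.8.3.2.
5. Ask the sponsor to reconcile the procedure and the definition within Protocol 7.10 on whether a seated reading can meet the OH definition. No clinical criterion is proposed here.

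**Cost.** Items 1 to 4 are SAP text and shell changes. The seated reading is already taken, so no new procedure is needed, but its position must be captured, and whether the case report form does so is not visible. The downside is a slightly less favourable OH display.
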